3.6. SUBJECT SELECTION

The study population will include approximately 300 subjects diagnosed with sub-optimally controlled T2DM who have moderate renal impairment. Eligible subjects who must be informed of the nature of the study and the potential risk and consent to participate in the study will be enrolled in clinical investigational sites in multiple countries.

3.6.1. Inclusion Criteria

Refer to protocol section 4.2 for inclusion criteria.

3.6.2. Exclusion Criteria

Refer to protocol section 4.3 for exclusion criteria.

3.7. DETERMINATION OF SAMPLE SIZE

Approximately 300 subjects will be randomized and equally allocated to receive bexagliflozin tablets, 20 mg, or placebo.

The sample size calculation for this study is based on a two group t-test with a two-sided significance at the 5% level and the following assumptions:

- 1) The placebo-corrected population mean change from baseline to Week 24 in HbA1c in the dose group of 20 mg will be -0.4%.
- 2) The pooled standard deviation for the change from baseline to Week 24 in HbA1c for the active and placebo groups will be 1.0%.

Under the above assumptions, an estimated sample size of 133 evaluable subjects per treatment arm yields approximately 90% power to detect a treatment difference between bexagliflozin and placebo. A sample size of 150 per arm has been selected to account for a potential 12% drop-out and to allow adequate safety evaluation. The total sample size for this study will be 300 subjects.

3.8. TREATMENT ASSIGNMENT & BLINDING

3.8.1. Treatment Assignment

The study will be conducted at investigative sites in multiple countries and will likely involve variable numbers of subjects at each site. Enrollment will be on a competitive basis but each site will be capped at 30 randomized subjects per site. Activation of investigational sites in each country will be centrally controlled by an Interactive Web Response System (IWRS).

Eligible subjects who complete the run-in period and meet all study inclusion/exclusion requirements will be randomized to receive investigational product. The treatment period for each study subject will start at randomization. Approximately 300 eligible patients will be randomized at the end of the run-in period in a 1:1 ratio to receive once daily bexagliflozin tablets for 24 weeks. Randomization will be stratified by HbA1c level (7.0 to 8.5% or 8.6 to 10.5%), screening anti-diabetic treatment regimen (insulin treated or not) and screening eGFR (30-44 or 45-59 mL/min/1.73 m²).

Subject randomization will be deactivated for all sites when the planned number of subjects is met. However, if a potential subject is in run-in period already and wishes to continue with the study, the subject will be allowed to continue and, if eligible, to be randomized.

3.8.2. Blinding

This is a double-blind placebo-controlled study. The sponsor, investigators, study coordinators, pharmacists, study subjects, and the cardiovascular adjudication committee members will be blinded to the study medication. Upon randomization, each subject will receive a subject randomization number and a drug kit assigned to the subject. To maintain blinding of the individual treatment assignment, the results of urinary glucose testing will not be made available to any study personnel or subjects.

If knowledge of the treatment is needed to manage the subject's condition, the investigator will contact the IWRS to obtain the treatment assignment. If unblinding occurs for any reason, the time and reason for breaking the blind will be recorded on CRF and the sponsor must be notified within 24 h.

A designated statistician who is not involved with the study operation will hold the treatment codes. The unblinded treatment information can be provided to the DSMB to facilitate the evaluation of any clinically important increase in the rate of a serious suspected adverse reaction or to the designated safety contact when the treatment information is required to determine if an expedited safety report must be submitted to regulatory agencies.

The treatment assignment will continue to be withheld from the cardiovascular adjudication committee members until all global investigational studies are completed and a meta-analysis to assess cardiovascular risk is conducted.

3.9. ADMINISTRATION OF STUDY MEDICATION

The following investigational products (IP) will be used for oral administration:

- Bexagliflozin tablets, 20 mg: tablets containing 20 mg of bexagliflozin
- Bexagliflozin tablets, placebo: tablets containing no bexagliflozin

Dosing with bexagliflozin tablets, 20 mg or placebo, will be based on randomized assignment. All study subjects will be instructed to self-administer tablets once daily in the morning prior to eating or drinking; the medication should be taken with water. There will be no change of dose during the treatment period.

On the day of each scheduled clinic visit, subjects must fast for a minimum of 8 hours prior to the collection of blood samples. During the fasting period, only water will be permitted.

3.10. STUDY PROCEDURES AND FLOWCHART

The activities that must be performed at each clinic visit listed below are presented in Table 1.

Table 1 Schedule of Events

Procedure	Screening	Run-in	Treatment						Follow-up
	V1	V2	V3	V4	V5	V6	V7	V8	V9
Time to Randomization	3 days -3 weeks to V2	-1	0	2	6	12	18	24	26
Informed Consent	X								
Screening for I/E Criteria	X		X						
Medical History	X								
Diet and Exercise Counseling		X							
Physical Examination			X						
Abbreviated Physical Examination	X					X		X	X
Weight	X		X		X	X		X	X
Vital Signs	X		X		X	X		X	X
Electrocardiography	X							X	
Diary and Glucometer Record Review			X	X	X	X	X	X	X
Dispensing Run-in Drug		X							
Randomization			X						
Dispensing Investigational Product			X			X			
Adverse Events & DKA Assessments		X	X	X	X	X	X	X	X
Concomitant Medication Assessments		X	X	X	X	X	X	X	X
Hematology	X		X		X	X		X	X
Serum Chemistry and Electrolytes	X		X		X	X		X	X
Glycemic Control	X		X		X	X		X	X
Serum Lipids	X		X			X		X	X
Urinalysis	X		X		X	X		X	X
UACR	X		X					X	X
Urine Pregnancy Test (WOCBP)	X		X		X	X		X	X
Population PK sampling					X	X			

A visit window of ± 3 days is allowed for all visits except Visit 3. V3 is the day of randomization and the basis for the visit window.

The study staff will contact each subject prior to a scheduled clinic visit to confirm the time of the visit and to remind the subject of proper fasting practice. A subject must be queried to assess compliance with a minimum of 8 hours fast prior to blood draw to ensure the FPG and triglycerides values can be accurately determined. If a subject has not fasted for a minimal of 8 h, the subject must return as soon as can be arranged (within 1 week) to provide a specimen after proper fasting.

4. ENDPOINTS

4.1. PRIMARY EFFICACY ENDPOINT

- Change from baseline to week 24 in HbA1c

4.2. SECONDARY EFFICACY ENDPOINTS

The key secondary endpoints are:

- Change from baseline to week 24 in body weight in subjects with baseline body mass index (BMI) $\geq 25 \text{ kg/m}^2$
- Change from baseline to week 24 in SBP in subjects with baseline SBP $\geq 130 \text{ mmHg}$ from baseline
- Change from baseline to week 24 in HbA1c in subjects with eGFR 45 to $59 \text{ mL/min/1.73 m}^2$
- Change from baseline to week 24 in HbA1c in subjects with eGFR 30 to $44 \text{ mL/min/1.73 m}^2$

Other Efficacy Endpoints

- Change in HbA1c over time in all subjects
- Proportion of subjects who reach target HbA1c of $<7\%$ over time
- Changes in FPG over time
- Proportion of $\geq 5\%$ reduction of body weight in subjects with baseline BMI $\geq 25 \text{ kg/m}^2$ at week 24
- Change in body weight in all subjects over time
- Changes in SBP and diastolic BP over time in all subjects
- Change in albuminuria (urine albumin creatinine ratio or UACR) categories at week 24 in all subjects and in subjects with baseline macroalbuminuria (UACR ≥ 300)

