6.2. KEY DEFINITIONS

6.2.1. Baseline Values

For safety endpoints, baseline is defined as the last non-missing measurement prior to the first dose of double-blind IP. For baseline demographics and efficacy endpoints, baseline is defined as the last non-missing value before the randomization date. These endpoints include HbA1c values, sitting SBP, height, body weight, BMI, FPG, eGFR, and UACR.

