Descriptive statistics for geometric mean, geometric coefficient of variation (gCV), median, Q1, Q3, minimum, and maximum of UACR values will be presented at baseline, and week 24 for all subjects and for baseline macroalbuminuria subjects (>300 mg/g). UACR data is left-skewed and will be natural log transformed first. Change in log transformed UACR from baseline to week 24 will be analyzed by ANCOVA model. The fixed effect will include region, baseline HbA1c level as continuous variable, screening anti-diabetic treatment regimen (insulin treated or other), baseline eGFR (<45 or ≥ 45 mL/min/1.73m²), and treatment. The log transformed baseline values will be used as covariate. Analysis will be repeated for baseline macroalbuminuria subjects. LS means for each treatment and the difference between treatments will be estimated at week 24. The adjusted geometric mean ratio of relative change from baseline in UACR (the ratio of the week 24 geometric mean and baseline geometric mean) and the corresponding two sided 95 % CI by treatment group will be calculated as the antilog of the LS mean and 95 % CI of log transformed values, converted to percentage. The adjusted geometric mean ratios of relative change from baseline in UACR for bexagliflozin vs. placebo (ratio of the two ratios obtained from previous steps) and their 95% CI will be calculated as the antilog of the LS mean differences and their 95% CI. Sample SAS code will be provided in Appendix 21.2.

8.2.2.3. Proportions of subjects with HbA1c of < 7% over time and proportion of $\geq 5\%$ reduction of body weight in subjects with baseline BMI ≥ 25 kg/m² at week 24

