13. CHANGE FROM ANALYSIS PLANNED IN PROTOCOL

In efficacy analysis in section 8, baseline eGFR categories, instead of screening eGFR, will be used as covariate and bases of subgroups analysis of key secondary analysis HbA1c in each eGFR groups. Albuminuria will be analyzed categorically, instead of change from baseline as continuous variable, due to some large outliers in the dataset.

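### Low-priority improvement: baseline UACR is taken from one of two pre-treatment samples, which costs precision and puts regression to the mean into the per-arm macroalbuminuria results

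*SAP*

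**What the plan says.** - **Endpoint.** SAP 4.2 lists "Change in albuminuria (urine albumin creatinine ratio or UACR) categories at week 24 in all subjects and in subjects with baseline macroalbuminuria", with macroalbuminuria given as UACR ≥ 300 and no unit. SAP 8.2.2.2 gives the limit as > 300 mg/g. Apart from 300, no category cut-off appears in the SAP text.
- **Baseline rule.** For efficacy endpoints, UACR named among them, SAP 6.2.1 says "baseline is defined as the last non-missing value before the randomization date".
- **Sampling.** Protocol Appendix 2 and SAP Table 1 schedule UACR at V1 and V3 before treatment, then at V8 (week 24) and V9 (week 26). SAP 3.10 makes V3 the day of randomization.
- **Week 24.** SAP 6.4 selects one record per analysis window. No repeat or confirmatory sample is required.
- **Analysis.** SAP 8.2.2.2 specifies an ANCOVA of change in log UACR with log baseline as covariate, reported per arm and as a ratio to placebo. It then says "Analysis will be repeated for baseline macroalbuminuria subjects". SAP 13 says "Albuminuria will be analyzed categorically, instead of change from baseline as continuous variable".
- **Status.** SAP 8.2.2 labels these endpoints exploratory, with no multiplicity adjustment.

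**The concern.** A subgroup picked because one measurement was high contains some subjects who were high by chance. Their next value tends to be lower whichever treatment they receive. Here the same noisy value is both the selection variable and the starting point for change. Per-arm percent change in UACR, and any per-arm count leaving macroalbuminuria, would therefore show improvement on placebo and too much improvement on drug. The LS means in 8.2.2.2 do not escape this: baseline adjustment protects the difference between arms, not the change within an arm of a subgroup selected on high values.

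The second cost is precision. A single-sample covariate explains less of the week 24 variance than a two-sample one, and the second sample is already collected. This applies to the all-subjects UACR analysis as well as to the subgroup.

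The rule is also unclear about which sample it means. Read literally, a value dated on the day of randomization is not before the randomization date, so V3 drops out and V1 becomes baseline. Protocol 9.4 (last measurement before the first double-blind dose) and SAP 9.4 (on or before Day 1, for laboratory data) point to V3.

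**Working it through.** **The plan's own figure.** The plan states no UACR quantity to reproduce. Its only calculation is for HbA1c: "an estimated sample size of 133 evaluable subjects per treatment arm yields approximately 90% power", with difference 0.4, SD 1.0 and two-sided 5%. The normal approximation gives 2 × (1.960 + 1.282)² × 1.0² / 0.4² = 131.3, so 132 per arm, and t-test power at 133 is 90.2%. It reproduces, but says nothing about UACR.

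**Assumed inputs (none is in the documents).** UACR is log-normal. Median 40-80 mg/g; between-subject log SD 1.4-1.7 (variance b); within-subject log SD 0.3-0.6 (variance w); no drug effect. Limit 300 at both times; its use at week 24 is itself an assumption.

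**Formulas.** With B the log baseline, Y the log week 24 value, ρ the V1-V3 noise correlation and d the SD of true individual change:
- V_B = b + w for one sample; b + w(1 + ρ)/2 for the mean of two logs
- V_Y = b + w + d²; Cov(B, Y) = b; r = b/√(V_B·V_Y)
- z_B and z_Y = ln(300/median) divided by √V_B and √V_Y
- P(below 300 at week 24 | baseline ≥ 300) = [Φ(z_Y) − Φ₂(z_B, z_Y; r)] / [1 − Φ(z_B)]
- Apparent fall in geometric mean = 1 − exp{−(1 − b/V_B)·√V_B·φ(z_B)/[1 − Φ(z_B)]}
- ANCOVA residual variance = V_Y − b²/V_B

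**Noisiest corner** (median 40, SDs 1.4 and 0.6): b = 1.96, w = 0.36, V_B = V_Y = 2.32, r = 0.845, z = 2.015/1.523 = 1.323.
- Below 300 at week 24: 39.4%. Apparent fall: 34.5%.
- Residual variance, one sample: 2.32 − 3.842/2.32 = 0.664.
- Two independent samples: V_B = 2.14, residual 2.32 − 3.842/2.14 = 0.525, a 21% reduction.
- ρ = 0.5: V_B = 2.23, residual 0.597, a 10% reduction.

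**Quietest corner** (median 80, SDs 1.7 and 0.3): b = 2.89, w = 0.09, V_B = V_Y = 2.98, r = 0.970, z = 1.322/1.726 = 0.766.
- Below 300 at week 24: 13.2%. Apparent fall: 6.8%.
- Residual variance: 0.177 with one sample, 0.134 with two independent samples, a 24% reduction.
- ρ = 0.5: residual 0.156, a 12% reduction.

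**Across the assumed ranges:**

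| Baseline UACR | Below 300 at week 24, no drug effect | Cut in residual variance against one sample |
|---|---|---|
| One sample | 13-39% (up to 40% with d = 0.4) | reference |
| Two samples, independent noise | 11-32% | 21-24% |
| Two samples, ρ = 0.5 | 12-36% | 10-12% |
| Two samples, ρ = 0.5 and d = 0.4 | 16-37% | 6-9% |

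The apparent geometric-mean fall is 7-34% with one sample and 3-20% with two independent samples. A variance cut of 21-24% narrows the confidence interval by 11-13% (√0.79 = 0.889, √0.76 = 0.872). A cut of 6-12% narrows it by 3-6%.

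**Sensitivity.** A wider grid (median 20-200 mg/g, between-subject log SD 1.2-2.0, within-subject CV 20-100%) puts the single-sample crossing share anywhere from 5% to 67%.

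**The case against.** The case for leaving the plan alone is substantial.

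- **No inference is at risk.** Selection precedes treatment and the noise is the same in both arms. The ANCOVA adjusts for log baseline and reports a ratio to placebo, and the endpoint is exploratory. This stands. A reader might infer that the estimated drug effect on UACR is biased; the documents do not support that.
- **The percentages are assumptions.** This stands. A reader might take 13-40% as a property of this trial, but the documents give no UACR distribution or variability.
- **Scoring at 300 is inferred.** This stands. A reader might conclude that the plan scores improvement against its own entry limit. The SAP text does not define the week 24 categories, and the table and figure shells are attachments outside the text reviewed.
- **Averaging does not cure regression to the mean.** This stands: 11-32% against 13-39% leaves most of the movement in place. The footnote deals with how per-arm figures are read; averaging mainly buys precision and a clear baseline.
- **The 21-24% gain is a best case.** This partly stands. V1 and V3 are only about 10 to 28 days apart, so their noise may be correlated, and true levels can drift over 24 weeks. The gain shrinks to 6-12% but does not vanish.
- **One last value is the SAP's uniform efficacy rule.** True, and departing from it for UACR is a small cost. But the rule as worded does not settle whether V1 or V3 is meant, so it needs an edit anyway.

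**Conclusion.** The point holds as a cheap, low-priority improvement to an exploratory analysis. The plan discards one of two pre-treatment UACR samples and relies on the remaining value for both subgroup entry and baseline adjustment. The consequences are a wider confidence interval than the data allow, and per-arm changes in the macroalbuminuria subgroup that cannot be read as treatment effects.

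The precision gain from using both samples is the firmer part: it stays positive with correlated V1-V3 noise and with true individual change. The crossing percentages are illustrative and rest wholly on the assumed medians and SDs. Three textual matters depend on no assumption: the literal baseline rule points to V1, the macroalbuminuria limit is written two ways, and SAP 13 replaces a continuous analysis that SAP 8.2.2.2 still specifies.

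**What to change.** 1. In SAP 6.2.1 and 8.2.2.2, define baseline UACR as the geometric mean of the V1 and pre-dose V3 values, or the single value if only one exists.
2. Use that value both to classify baseline macroalbuminuria, with one stated limit (≥ 300 mg/g), and as the log-baseline covariate.
3. Keep the log-UACR ANCOVA of 8.2.2.2 as the between-arm estimate and reword SAP 13 to agree with it. If a category table is kept, state its cut-offs.
4. Footnote the subgroup outputs: per-arm movement out of the selected category includes regression to the mean, and only the between-arm contrast estimates a drug effect.

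The cost is SAP wording and one derived variable; no sample or visit is added. V9 should not serve as confirmation, since it falls two weeks after treatment ends. The downside is that the UACR baseline would be derived differently from the other efficacy baselines.

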4.3. SAFETY ENDPOINTS

- Adverse events (AE), including AE of special interest (urinary tract infections [UTI], genital mycotic infection [GMI], diuretic effects, hepatotoxicity, hypoglycemia, MACE, fractures, malignancy, hypersensitivity reactions,

hypotensive episodes, acid-base disorders, diabetic ketoacidosis [DKA], renal failure events and amputations)

- Laboratory testing, including hematology, serum chemistry, urinalysis, urinary electrolytes and creatinine
- 12-lead ECG
- Vital signs
- Physical examination
- Concomitant medication use

4.4. OTHER ENDPOINTS

- Measurement of bexagliflozin plasma concentration as a function of time from dosing (sparsely sampled).

5. ANALYSIS SETS

5.1. SCREENED ANALYSIS SET

The Screened Analysis Set will include all subjects who have signed the informed consent forms and completed the eligibility screening prior to randomization. The screened analysis set will consist of both enrolled subjects and subjects who do not meet the eligibility criteria. This set will be used for summaries of subject disposition.

5.2. SAFETY ANALYSIS SET

All subjects who are randomized and take at least one dose of the double-blind IPs will be included in the Safety Analysis Set. Safety analyses will be based on the treatment that a subject takes upon randomization. The Safety Analysis Set is the primary analysis set for safety evaluation.

5.3. INTENTION-TO-TREAT ANALYSIS SET

All subjects who are randomized will be included in the Intention-to-Treat (ITT) Analysis Set. All analyses of the ITT Analysis Set will be based on each subject's randomized assigned treatment. The ITT analysis set will serve as the primary set for the efficacy analyses.

5.4. PER PROTOCOL ANALYSIS SET

The Per Protocol (PP) Analysis Set will include all subjects in the ITT Analysis Set who meet the study eligibility requirements and have no major protocol deviations that affect the validity of the efficacy measurements. Detailed protocol deviations that may result in subject or visit exclusion from the PP Analysis Set are described in Section 5.5. The PP Analysis Set will serve as the secondary set for efficacy assessment.

5.5. PROTOCOL DEVIATIONS

Protocol deviations will be captured during the study conduct. Some of the examples of major deviations that may result in subject exclusion from the PP Analysis Set are given in Table 2. The list of deviations will be reviewed before unblinding and major protocol deviations that, in the opinion of the medical monitor, could affect the primary and secondary variables will be determined.

Table 2 Some Possible Types of Major Protocol Deviations That Lead to Subject or Visit Exclusion from PP analysis set.

Category	Criteria	Exclusion
Inclusion/Exclusion Criteria		
Ineligible subject is enrolled	- Subjects not satisfying HbA1c inclusion criteria - Subjects not satisfying eGFR inclusion criteria (inclusion #4 and #7) - Treated with SGLT2 within 3 months of screening	Subject exclusion
Prior or Concomitant Medication Restrictions		
Use of another SGLT2 inhibitor	Use of an SGLT2 inhibitor as the rescue medication for hyperglycemia	Visit exclusion [exclude data post SGLT2 starts]
Use of new Diuretic medication	Initiate of new diuretic medication within 12 weeks of randomization	Visit exclusion [exclude data post initiation of a new diuretic]
Randomization/Blinding		
Unblinding	Blind was broken (requested in IWRS)	Visit exclusion [exclude data post blind broken]
Dosing Non-Compliance	-Subject missed more than 50% of the investigational product doses between week 12 and week 24	Subject exclusion

6. GENERAL ASPECTS FOR STATISTICAL ANALYSIS

6.1. GENERAL METHODS

Statistical methodology and analyses are in accordance with the principles outlined by the ICH E9 guidelines. All statistical analyses will be conducted using SAS statistical software version 9.3 or higher.

Tables, listings and figures (TLFs) will be produced in accordance with the principles outlined by the ICH E3 guidelines. For most summary statistics, data will be analyzed by the following treatment groups: Bexagliflozin 20 mg and Placebo. All available data will be presented in the subject listings.

Data summaries will use descriptive statistics (number of subjects [n], mean, standard deviation [SD], Q1, median, Q3, minimum, and maximum) for continuous variables, and frequency and percentage of subjects for categorical and ordinal variables, unless otherwise specified.

Unless otherwise specified, all tests will be two-sided using a 0.05 level of significance. All confidence intervals (CIs) will be two-sided 95% CIs.

The analysis visit window will be assigned to data collection. One selected data point per visit will appear in summary tables and figures. Refer to section 6.4 for details. All visit assessment data will be included in shift tables and will appear in the subject listings.

6.2. KEY DEFINITIONS

6.2.1. Baseline Values

For safety endpoints, baseline is defined as the last non-missing measurement prior to the first dose of double-blind IP. For baseline demographics and efficacy endpoints, baseline is defined as the last non-missing value before the randomization date. These endpoints include HbA1c values, sitting SBP, height, body weight, BMI, FPG, eGFR, and UACR.

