6.8 Body Weight

Total body weight will be determined in every clinical visit except visit V2. The weight must be determined using a scale that is calibrated. Every effort should be made to use the same scale throughout the study duration.

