6.11.1.3 Renal function testing

Serum creatinine will be measured as part of the serum chemistry at the scheduled clinical visits. UACR will be determined at time points specified in the schedule of laboratory tests ([Appendix 2](#)).

At the screening and randomization visits (V1 and V3), serum samples must be submitted to the central laboratory for serum creatinine testing. The serum creatinine value determined at the screening visit by the central laboratory will be the value for assessing eligibility, assigning stratum at randomization, and the central lab serum creatinine value determined at the randomization (V3) will be the baseline value for the data analyses.

During the study period, if a rapid turnaround time is necessary for clinical assessment of a potential kidney injury, testing from local laboratories should be used.

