6.14 Randomization

Subjects who have met all the inclusion criteria and none of the exclusion criteria at the end of the run-in period will be randomized to receive investigational product using the IWRS. A randomization number and a drug kit number will be assigned to the subject. The subject should be instructed to refrain from taking the run-in medication on the day of randomization. The date and time of the last dose of run-in drug should be recorded. Subject will take the first dose of the double-blind study drug at the clinic.

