9 PLANNED STATISTICAL METHODS

9.1 General Considerations

The following sections provide a summary of the planned analysis of the trial but a complete statistical analysis plan will be developed as a separate document and will be the final plan. All statistical analyses will be performed using Version 9.2 or later of Statistical Analysis Software (SAS®).

In general, descriptive statistics (number of subjects [n], mean, standard deviation [SD], Q1, median, Q3, minimum, and maximum) will be presented for continuous variables, and frequency and percentage for categorical variables.

Unless otherwise specified, all tests will be two-sided using a 0.05 level of significance. All confidence intervals (CIs) will be two-sided 95% confidence intervals.

The primary superiority test on lowering of HbA1c at week 24 from baseline for bexagliflozin when compared to placebo will be conducted at 0.05 level of significance. If it is successful, the following hierarchical testing strategy will be followed in testing secondary efficacy end points in order to preserve experiment-wide type I error at 0.05:

1. Superiority test of the change in body weight in subjects with baseline body mass index (BMI) ≥ 25 kg/m² in the bexagliflozin group compared to the placebo group
2. Superiority test of the change in systolic blood pressure (SBP) over time in subjects with SBP ≥ 130 mmHg in the bexagliflozin group compared to the placebo group
3. Superiority test of the change in HbA1c over time in subjects with eGFR 45 to 59 mL/min/1.73m² in the bexagliflozin group compared to the placebo group
4. Superiority test of the change in HbA1c over time in subjects with eGFR 30 to 44 mL/min/1.73m² in the bexagliflozin group compared to the placebo group

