9.4 Demographics and Baseline Characteristics

Demographic and baseline characteristics will be summarized descriptively based on the ITT and PP (if applicable) analysis sets for each treatment group as well as for all subjects combined. Key variables include age, gender, race, ethnicity, baseline HbA1c values, blood pressure, body weight, body mass index (BMI in kg/m²), fasting plasma glucose level, eGFR, and anti-diabetic treatment status at screening (including type of therapy used [treatment naïve, metformin, sulfonylurea, DPP-4 inhibitor, alpha-glucosidase inhibitor, GLP-1 agonist, insulin]). In general, baseline measurement is defined as the last measurement prior to the first dose of double-blind medication.

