7.3. DEMOGRAPHIC AND OTHER BASELINE CHARACTERISTICS

Demographic characteristics include age, gender, race, ethnicity, and country and region of investigational site. Baseline characteristics will include baseline HbA1c values, blood pressure, height, body weight, BMI, FPG, eGFR, eGFR baseline groups (<45 or ≥45 mL/min/1.73m²), UACR, duration of diabetes from diagnosis to the date of informed consent, and prior anti-diabetic treatment status at screening. Baseline will be defined as the last non-missing value prior to randomization. Randomization stratification related factors will be summarized based on data collected on CRF or by lab. They include screening HbA1c groups (7.0 to 8.5% vs. 8.6 to 10.5%), screening anti-diabetic treatment status (insulin treated, other), screening eGFR values, and screening eGFR groups (30-44 or 45-59 mL/min/1.73m²). Stratification factors from IWRS will be summarized if they are not consistent with CRF or lab values. Summary descriptive statistics by treatment will include counts and percentages for discrete variables and estimation of means, standard deviations, medians, inter-quartile range (Q1, Q3), minimum, and maximum for continuous variables. Subjects' baseline

demographic and personal baseline characteristics will be summarized by treatment group and overall for subjects in the Safety, ITT, and PP Analysis Set. Subject age will be the age at date of informed consent collected from CRF.

Demographics data and randomization stratification factors will be presented in a data listing. Prior treatment will be listed along with all medications.

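### SAP 6.2.1 takes the efficacy baseline from before the randomization date, which read literally selects the screening visit (V1) rather than the randomization visit (V3)

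*SAP*

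**What the plan says.** SAP 6.2.1 has two baseline rules. Safety endpoints take the last value before the first double-blind dose. For the rest, "For baseline demographics and efficacy endpoints, baseline is defined as the last non-missing value before the randomization date"; the variables listed are HbA1c, sitting SBP, height, weight, BMI, FPG, eGFR and UACR.

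On timing, SAP 3.10 says "V3 is the day of randomization and the basis for the visit window", and protocol section 7 agrees. V2 supplies no efficacy value. Protocol 6.8 says "Total body weight will be determined in every clinical visit except visit V2", and protocol Appendices 1 and 2 show no vital signs or laboratory tests at V2.

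The protocol sets baseline in two places. For creatinine, 6.11.1.3 says "the central lab serum creatinine value determined at the randomization (V3) will be the baseline value for the data analyses"; the V1 value serves eligibility and stratum. In general, 9.4 says "baseline measurement is defined as the last measurement prior to the first dose of double-blind medication", and 6.14 places that dose at V3: "Subject will take the first dose of the double-blind study drug at the clinic".

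Elsewhere in the SAP, 7.3 says "Baseline will be defined as the last non-missing value prior to randomization". Section 9.4 takes the latest laboratory value up to and including Day 1. Section 13 declares that baseline eGFR categories replace screening eGFR, both as covariate and as the basis of the eGFR key secondary sets. Protocol 9.1 makes the SAP govern: "a complete statistical analysis plan will be developed as a separate document and will be the final plan".

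**The concern.** A strict before, applied to a date, excludes everything measured on that date, so a programmer who follows 6.2.1 to the letter takes the wrong visit. The wording can even look deliberate, because the preceding sentence gives safety endpoints a different rule. SBP would then have a V1 baseline in the efficacy tables and a V3 baseline in the safety tables.

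The rule feeds the primary change score and its covariate, the eGFR factor in the model, and entry to the BMI ≥25, SBP ≥130 and two eGFR key secondary sets. Those sets are tested in a hierarchy, so their membership should be beyond argument before unblinding.

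**Working it through.** **1. Which visit does each rule select?**

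| Source | Rule | Scheduled visit selected |
|---|---|---|
| SAP 6.2.1, efficacy | before the randomization date | V1 |
| SAP 6.2.1, safety | before first double-blind dose | V3 |
| Protocol 9.4 with 6.14 | before first double-blind dose, taken at V3 | V3 |
| Protocol 6.11.1.3 | V3 creatinine (creatinine only) | V3 |
| SAP 7.3 | before randomization, the event | V3 admitted, since V3 samples precede that step |
| SAP 9.4 | up to and including Day 1 | V3 |
| SAP 13 | baseline eGFR replaces screening eGFR | V3, otherwise the switch is nearly empty |

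An unscheduled sample between V1 and V3 would displace V1 under the literal rule. Height is scheduled only at V1, so it is the same under either reading.

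**2. Gap between V1 and V3.** V1 to V2 is 3 to 21 days (protocol 7.1) and the run-in is 7 to 9 days (protocol 3.2.2). The gap is 3 + 7 = 10 to 21 + 9 = 30 days, before the ±3-day window.

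**3. The plan's own figure.** SAP 3.7 uses a difference of 0.4, SD 1.0 and two-sided 5%. The noncentral t distribution gives power 0.899 at 132 per arm and 0.901 at 133, so the stated 133 for 90% reproduces.

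**4. Precision of the primary analysis.** Assumptions not in the documents: equal variance σ² at each visit, SD of change from V3 of 1.0, correlation r3 of V3 HbA1c with Week 24 of 0.60 or 0.70, and V1 correlation r1 lower by 0.01 to 0.06. The MMRM is approximated by a baseline-adjusted Week 24 comparison with 133 per arm.

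σ² = 1/[2(1 − r3)], which is 1.25 or 1.667; residual SD = √[σ²(1 − r²)].

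| r3 | r1 | Residual SD, V3 / V1 | Power, V3 / V1 | CI width, V1 ÷ V3 |
|---|---|---|---|---|
| 0.60 | 0.59 | 0.894 / 0.903 | 0.953 / 0.950 | 1.009 |
| 0.60 | 0.57 | 0.894 / 0.919 | 0.953 / 0.943 | 1.027 |
| 0.60 | 0.54 | 0.894 / 0.941 | 0.953 / 0.932 | 1.052 |
| 0.70 | 0.69 | 0.922 / 0.934 | 0.941 / 0.936 | 1.014 |
| 0.70 | 0.67 | 0.922 / 0.958 | 0.941 / 0.924 | 1.040 |
| 0.70 | 0.64 | 0.922 / 0.992 | 0.941 / 0.906 | 1.076 |

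**5. Membership of the key secondary sets.** These are simulations with 4,000,000 draws; all variability inputs are assumed.

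- eGFR: true value uniform 25–65 or normal (45, SD 8); history, V1 and V3 each equal true × (1 + CV × normal), CV 5% or 8%. Subjects are kept if history and V1 are both in 30 to <60 and within 20% of each other (inclusion criteria 4 and 7). The share crossing 45 between V1 and V3 is 0.092 and 0.149 (uniform), and 0.135 and 0.207 (normal). The share below 45 differs between the visits by at most 0.4 percentage points. V3 eGFR is below 30 in 0.5–3.0% and at or above 60 in 1.1–4.9%, together 1.6–7.8%, or 5 to 23 of 300.
- SBP: between-subject SD 14, visit SD 8 or 10, mean 130 or 138 mmHg. The share on opposite sides of 130 is 0.20–0.27. The share at or above 130 agrees between visits within 0.1 percentage points.
- BMI: mean 26–32, SD 4–5, weight CV 0.7–1.5%. At most about 4% cross 25.

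**The case against.** The strongest reply is that nobody would be misled. Protocol 9.4 and 6.11.1.3, SAP 9.4, and the SAP text that calls week 0 the baseline visit all point to V3, and SAP 13 declares no move to a screening baseline. The SAS code and table shells are attachments that are not shown, so the programming may already be right. This stands as to intent: it makes the matter a wording error. It does not remove the need for the fix, because the governing document's operative sentence still selects V1.

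The reply is also right that the precision loss follows from the assumed drop in correlation. Protocol 6.19 says HbA1c reflects about three months, and V1 and V3 are at most about 30 days apart on stable therapy. A drop of only 0.01 is plausible and widens the interval by about 1%.

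Four stronger readings are tempting, and the documents do not support them.

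- *The SAP has adopted a rival screening baseline.* SAP 13 does not say so, and its eGFR switch presupposes that screening and baseline differ.
- *SAP 7.3 contradicts 6.2.1.* It refers to the event, not the date, so it admits V3 and supports it.
- *The primary comparison is biased or underpowered.* Both candidate baselines precede treatment, and power stays above 90% in every scenario above.
- *Subjects with V3 eGFR below 30 or at least 60 drop out of both eGFR sets.* SAP 13 makes the baseline categories the basis of those sets, and SAP 7.3 and 8.1.1 define them as <45 and ≥45. Subjects would be lost only if the 30–44 and 45–59 labels in 8.1.3 and 8.2 overrode section 13.

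**Conclusion.** The point holds as a wording error in the rule that fixes the efficacy baseline. As written, SAP 6.2.1 selects V1, while the protocol and the rest of the SAP indicate V3. The explicit V3 statement covers creatinine only; for the other variables V3 follows from protocol 9.4.

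The consequence is modest. A literal implementation would cost about 1–8% in confidence interval width, shift the within-arm changes, and exchange some members of the key secondary sets (9–21% at eGFR 45, 20–27% at SBP 130) with almost no change in their sizes. These figures rest on assumed correlations, SDs and CVs; the date logic does not. It should be corrected because the rule governs the primary endpoint and the correction costs almost nothing.

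The eGFR labels and the table title are secondary: they did not follow the switch in SAP 13, and they leave the placement of subjects with V3 eGFR outside 30 to <60 less clear than it should be.

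**What to change.** Before unblinding:

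1. In SAP 6.2.1 define the efficacy baseline as *the last non-missing value on or before the randomization date and before the first double-blind dose (normally V3); for randomized subjects never dosed, on or before the randomization date*. Use the same words in SAP 7.3.
2. If V1 really is intended, declare it in SAP 13 as a departure from protocol 6.11.1.3 and 9.4.
3. Align the eGFR labels in SAP 8.1.3 and 8.2 with the <45 and ≥45 baseline categories, as section 13 implies, so that every subject is clearly placed. Retitle Table 14.2.1.11, which still refers to screening eGFR.
4. Check the baseline HbA1c subgroup in SAP 8.1.3 in the same way: it keeps the screening stratum bounds (7.0–8.5% and 8.6–10.5%), which a V3 value may fall outside.

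The cost is one phrase in two places, a few labels and one table title. No new data are needed and the sample size does not change.
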